### 7. GENERAL CONSIDERATIONS

Post-text Tables and Listings will be prepared in accordance with the current ICH Guidelines. The header of each Table and Listing will include the sponsor's name and the study number. The information and explanatory notes to be provided in the "footer" or bottom of each Table and Listing will include the following information:

- 1. Date and time of output generation.
- 2. SAS® program name, including the path that generates the output.
- 3. Any other output specific details that require further elaboration.

In general, tables will be formatted with a column displaying findings for all patients combined. Row entries in tables are made only if data exist for at least one (1) patient (*i.e.*, a row with all zeros will not appear). The only exception to this rule applies to tables that list the termination status of patients (*e.g.*, reasons for not completing the study). In this case, zeros will appear for study termination reasons that no patient satisfied. The summary tables clearly indicate the number of patients to which the data apply, and unknown or not performed are distinguished from missing data. Tables, Listings, and Figures will provide the units of measurement, unless there are no units. Results recorded at single times during the study will be presented using the *Level 1* displays for the ITT Population; the example structure is presented below.

Level 1a Display

Parameter	Device Generation 1 / 600	Device Generation 1 / 600	Device Generation 2 / 750	All
and Statistic	Volts / Single Treatment	Volts / Double Treatment	Volts / Double Treatment	Patients
Age				
Sex				

Level 1b Display

		zever re zaspawy	
	Device Generation 1 / 600 Volts	Device Generation 1 / 600 Volts / Double	All
Parameter and Statistic	/ Single Treatment	Treatment and Device Generation 2 / 750 Volts /	Patients
		Double Treatment	
Age			
Sex			

The Level 2 displays will be used for summarizing the incidence of AEs. An example of the layout for AEs by severity is presented below.

Level 2a Display

System Organ Class	Device Generation 1 / 600	Device Generation 1 / 600	Device Generation 2 / 750	All
Preferred Term	Volts / Single Treatment	Volts / Double Treatment	Volts / Double Treatment	Patients
SOC				
PT				

Level 2b Display

System Organ Class	Device Generation 1 / 600 Volts	Device Generation 1 / 600 Volts / Double Treatment and Device Generation 2 / 750 Volts / Double Treatment	All
Preferred Term	/ Single Treatment		Patients
SOC PT			

The Level 3 display will be used for summarizing the parameters recorded multiple times during the follow-up visits. An example of the layout is presented below; rows will be repeated for all visits where a measurement is recorded using the expanded time windows.

Version 1.0 Confidential Page 18 of 42

Level 3a Display

			ou Dispiuj		
Parameter and Statistic	Observation Time	Device Generation 1 / 600 Volts / Single Treatment	Device Generation 1 / 600 Volts / Double Treatment	Device Generation 2 / 750 Volts / Double Treatment	All Patients
HbA1c	Baseline				
HbA1c	Post-Procedure Visit xxx				
HbA1c	Change from Baseline				

Level 3b Display

Parameter and Statistic	Observation Time	Device Generation 1 / 600 Volts / Single Treatment	Device Generation 1 / 600 Volts / Double Treatment and Device Generation 2 / 750 Volts / Double Treatment	All Patients
HbA1c	Baseline			
HbA1c	Post-Procedure Visit xxx			
HbA1c	Change from Baseline			

There will be 2 sets of comparative analyses prepared, each predicated on different combinations of device generation, voltage, and single vs. double treatment. The planned comparisons are outlined below.

### Comparison Set 1

Device Generation 1 / 600 Volts / Single Treatment vs.

Device Generation 1 / 600 Volts / Double Treatment vs.

Device Generation 2 / 750 Volts / Double Treatment

#### Comparison Set 2

Device Generation 1 / 600 Volts / Single Treatment vs.

Device Generation 1 / 600 Volts / Double Treatment plus Device Generation 2 / 750 Volts / Double Treatment

Supportive individual patient data Listings will be sorted and presented by site number, patient number and visit date, if applicable. Listings will also include the number of days relative to the DMR index procedure. Specific algorithms are discussed for imputing missing or partially missing data, if deemed appropriate, under specific data topics. Imputed or derived data will be flagged in the individual patient data Listings. Imputed data, restricted to dates, will not be incorporated into any raw or primary datasets from the electronic capture system. The imputed data will be retained in the derived / analysis datasets.

Summary statistics will consist of the number and percentage of responses or counts at each level for categorical variables (e.g. race). For continuous variables, and the sample size (n), mean, median, standard deviation (SD), minimum, and maximum values will be presented.

All mean and median values will be formatted to one more decimal place than the measured value. Standard deviation values will be formatted to two more decimal places than the measured value. Minimum and maximum values will be presented with the same number of decimal places as the measured value.

The number and percentage of responses will be presented in the form XX (XX.X%).

Version 1.0 Confidential Page 19 of 42

- All summary tables will include the analysis population sample size (i.e., number of patients).
- Relative Study Day 1 is defined as the day the patient underwent the DMR study procedure. All study days are determined relative to the day the patient underwent the DMR study procedure.
- Baseline values will be defined as those values recorded immediately prior to the DMR study procedure.
- Change from baseline for ratio data will be calculated as follows:

### Change = Post-Procedure value / baseline value.

• Change from baseline for differences will be calculated as follows:

### Change = Post- Procedure value - baseline value.

- Missing data may have an impact upon the interpretation of the trial data. However, given the feasibility nature of this study, coupled with the number of patients within a Comparison Set, multiple imputation will not be attempted. The primary presentation of the results will be based on the observed data. A methodology is defined in this section for addressing missing dates.
- Date variables will be formatted as DDMMMYYYY for presentation; SAS Date9. format.
- Months will be converted to days by dividing by 30.42 and rounding up to achieve an integer value.
- SAS® Version 9.4 will be the statistical software package used for all data analyses.
- All data from this study will be presented in a listing.
- Table and listing numbering will follow ICH guidelines for post-text table and listing numbering.

For Adverse Event reporting, which includes primary and secondary variables, the primary analysis will be based on Patient counts (e.g., the number and percentage of Patients with events among the total number of Patients). The data will be presented in the format of p% (x/N) [e], with p and x being the percentage and number of Patients with events, respectively, N being the sample size of the analysis population, and e being the total number of events occurred in the x Patients. Asymptotic confidence limits will be presented based on the normal approximation to the binomial distribution for differences in proportions. Exact confidence intervals will be used for all other presentations.

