12.4 Statistical Analysis

12.4.1 General Statistical Considerations

Analyses will be performed according to the general principles and directions outlined in these methods.

- Continuous data will be summarized using descriptive statistics: mean, standard deviation, median and range or interquartile range. Categorical variables will be summarized using frequency counts and percentages.
- For events which can occur multiple times in a single subject (e.g., adverse events), summaries
 will be comprised of the number and percentage of subjects with an event and the total number of
 such events. The proportion of subjects with events will be considered primary for analysis
 purposes.
- In general, available data will be used for all analyses, and missing data will not be replaced or
 otherwise imputed in summaries and analyses of study outcomes. However, to avoid biasing
 results due to confounding therapies, effectiveness data collected after an identified initiation of
 rescue medication for hyperglycemia will be replaced by the last value collected prior to such
 rescue intervention.
- Although the study is not explicitly powered to test *a priori* statistical objectives, comparisons citing p-values may be made between baseline metrics to values collected post-intervention, and between subgroups including the two treatment arms. In such cases, p-values will be presented using two-sided tests at a 0.05 level of significance or equivalently one-sided tests at a 0.025 level of significance.

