12.4.3 Primary Endpoint Analysis

The primary endpoint of the study is the proportion of participants experiencing one or more device- or procedure-related serious adverse events within 12 weeks post-procedure. The analysis will be performed using the ITT population, then tabulated and reported for each treatment arm and overall. Fisher's exact test will be used to assess differences which may be present between groups

Additionally, an overall summary of AEs will be provided including the number of events and percent of participants with any AEs, SAEs, and UADEs. For each type of event, the number of events and number and percent of participants with the event will be provided. Separate summaries of all adverse events will be summarized by seriousness and by relationship to device and procedure.

Only events occurring at or after the index procedure will be counted for the purpose of safety analysis. Events occurring prior to the index procedure will be considered as medical history.

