# 9.1. Analysis of the Primary Safety Endpoint

Each table number and population will clearly state; results will be presented using the Table 1a design. Results will be tabulated based on the number of patients experiencing one or more device-related or procedure-related serious adverse events at 12 weeks post-procedure.

The statement of the primary research question that will be addressed is as follows:

What percentage of the patients in the ITT population experienced one or more device-related or procedure-related serious adverse events within 12 weeks (84 days) of the index study procedure?

The statement of the secondary research question is specific below:

Is there a difference in the percentage of patients in the ITT population who experienced one or more device-related or procedure-related serious adverse events within 12 weeks (84 days) of the index study procedure based on the generation of the device, voltage, and single vs. double treatment?

The following model will be used to compare the groups identified within each Comparison Set. The dependent variable is the classification of each patient relative to experiencing a device-related or procedure-related serious adverse events at within 12 weeks (84 days) of the index study procedure [variable: DRPRSAE]. Contrast statements will be used to derive the estimates for each pair-wise comparison of a group.

Version 1.0 Confidential Page 32 of 42

```
PROC GLIMMIX DATA=COMP_SET_1;
    CLASS COMP_SET_1_GROUP;
    MODEL DRPRSAE = COMP_SET_1_GROUP / DIST=BINARY LINK=LOGIT SOLUTION;
    RANDOM INTERCEPT / SUBJECT=SUBJID_N;
    LSMEANS TRTAN / DIFF CL;
RUN;
```

Sensitivity analyses will be performed using the FAS and PP populations. Results will be presented in the analysis table 14.4.1 entitled Summary of the Device-Related or Procedure-Related Serious Adverse Events Within 12 weeks (84 days) of the index study procedure (ITT Population) and table 14.4.1.1 entitled Summary of the Device-Related or Procedure-Related Serious Adverse Events Within 12 weeks (84 days) of the index study procedure (FAS Population) and table 14.4.1.2 entitled Summary of the Device-Related or Procedure-Related Serious Adverse Events Within 12 weeks (84 days) of the index study procedure (PP Population). Listing 16.4.11 entitled Adverse Events provides supportive data for Tables 14.4.1, 14.4.1.1, and 14.4.1.2 will be sorted by site number and patient number.

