### 10.1.3. Summaries of Adverse Events

All summaries of adverse events will be based on events that occurred during the study and reported for the ITT population. Adverse events will be mapped to preferred terms and body systems using the Medical Dictionary for Regulatory Activities (MedDRA) coding dictionary. The number and percentage of patients experiencing 1 or more adverse events will be presented by preferred term using counts, percentages, and 2-sided 95% exact binomial confidence intervals. The relationship of the adverse event relative to the *device* and *procedure* will be presented

Version 1.0 Confidential Page 37 of 42

separately. The number and percentage of patients experiencing 1 or more events will be presented by the event description using counts, percentages, and 2-sided 95% exact binomial confidence intervals.

Table 14.3.2 entitled *Overall Summary of Adverse Events (ITT Population)* contains the primary presentation of the adverse event data, independent of the type of event. This table is prepared without regard to causality or relationship to the study procedure or device. Patients will be counted only once for each event type; multiple occurrences of the same event type for a patient will only be counted once. Event types will be displayed alphabetically. The overall incidence of adverse events will be summarized using counts, percentages, and 2-sided 95% exact binomial confidence intervals.

Table 14.3.3 entitled Summary of Adverse Events by Event Type (ITT Population) contains the primary presentation of the adverse event data. This table is prepared without regard to causality or relationship to the study procedure or device. Patients will be counted only once for each event type; multiple occurrences of the same event type for a patient will only be counted once. Event types will be displayed alphabetically. The overall incidence of adverse events will be summarized using counts, percentages, and 2-sided 95% exact binomial confidence intervals.

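### Normal-approximation limits for differences in proportions are unsafe for contrasts of 3 v 7 v 10 and 3 v 17 patients: zero width when neither group has an event, and poor coverage at many unequal rates

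*SAP*

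**What the plan says.** The closing paragraph of SAP section 7 (General Considerations) deals with adverse event reporting and says that this includes primary and secondary variables. It sets the rule for intervals: "Asymptotic confidence limits will be presented based on the normal approximation to the binomial distribution for differences in proportions". The next sentence reads "Exact confidence intervals will be used for all other presentations". Neither sentence mentions a continuity correction, a zero-cell rule or a confidence level.

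SAP section 3 gives the group sizes: 3 patients (generation 1, 600 V, single treatment), 7 (generation 1, 600 V, double) and 10 (generation 2, 750 V, double). Section 7 then states: "There will be 2 sets of comparative analyses prepared, each predicated on different combinations of device generation, voltage, and single vs. double treatment". Set 1 compares the three groups with one another. Set 2 compares the group of 3 with "Device Generation 1 / 600 Volts / Double Treatment plus Device Generation 2 / 750 Volts / Double Treatment", which is 7 + 10 = 17 patients.

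SAP 9.1 puts a between-group question on the primary endpoint: "Is there a difference in the percentage of patients in the ITT population who experienced one or more device-related or procedure-related serious adverse events". Its model is a logistic one. Protocol 12.4.3 has a different tool for the same contrast: "Fisher's exact test will be used to assess differences which may be present between groups".

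**The concern.** The SAP uses exact intervals generally and makes an exception for contrasts between very small groups, where the normal approximation is weakest. The usual (Wald) variance uses the observed proportions. A group with 0% or 100% therefore contributes no variance, even if it holds three patients. If both groups are at 0%, the interval is a single point.

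Two misleading results could follow. If no related serious event occurs, the report could give a difference of 0 with limits 0 to 0, which reads as certainty. In other cases an interval could exclude zero while Fisher's exact test on the same counts shows nothing. The study has no formal hypothesis tests (SAP section 9), so intervals carry much of the information on how the regimens differ.

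**Working it through.** The documents state no coverage or power figure, so there is none to reproduce. The counts agree: 3 + 7 + 10 = 20 and 7 + 10 = 17.

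**Assumptions**
- The level is 95% two-sided. This is inferred from SAP 10.1.3 ("2-sided 95% exact binomial confidence intervals") and Protocol 12.4.1 ("p-values will be presented using two-sided tests at a 0.05 level of significance").
- There is no continuity correction, because none is mentioned.
- True event rates are assumed, because the documents give none. In each pair, the first rate belongs to the smaller group.

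**Formula.** d ± 1.96 × √[p₁(1−p₁)/n₁ + p₂(1−p₂)/n₂], where d = p₁ − p₂ and p₁, p₂ are the observed proportions.

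**No events in either group.** Both variance terms are 0, so the limits are [0, 0] for every contrast. For 3 v 17 with a 5% risk in both groups, the chance of this is 0.95²⁰ = 0.358, or 36%. The Newcombe score limits at 0 v 0 run from −1.96²/(n₂ + 1.96²) to +1.96²/(n₁ + 1.96²). For 0/3 v 0/17 that is −3.84/20.84 to +3.84/6.84, or −18 to +56 points.

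**Coverage.** Each entry is the sum of the binomial probabilities of all outcomes (x₁, x₂) whose interval contains the true difference, in percent.

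| Contrast | 15 v 5 | 5 v 15 | 5 v 2 | 5 v 5 | 10 v 10 | 70 v 70 |
|---|---|---|---|---|---|---|
| 3 v 7 | 50.0 | 71.0 | 24.9 | 99.2 | 96.7 | 83.7 |
| 3 v 10 | 34.8 | 81.9 | 29.3 | 98.4 | 92.8 | 73.3 |
| 7 v 10 | 67.2 | 84.5 | 42.6 | 99.0 | 95.6 | 90.3 |
| 3 v 17 | 35.9 | 91.3 | 38.1 | 98.7 | 92.6 | 69.6 |

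The low figure at 15 v 5 has a simple cause. The group of 3 has no event with probability 0.85³ = 0.614. For 3 v 17 the upper limit is then at most about +5 points (reached at 0/3 v 1/17), below the true +10. Coverage therefore cannot exceed 1 − 0.614 = 38.6%. At equal low rates coverage is high partly because [0, 0] happens to contain the true difference of 0.

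**An interval that contradicts the test.** For 3/3 v 10/17:
- d = 1 − 0.588 = 0.412.
- Standard error = √(0 + 0.588 × 0.412/17) = 0.119.
- Limits = 0.412 ± 0.234, or +18 to +65 points, which exclude zero.
- Fisher's two-sided p = 0.52, and the Newcombe limits are −18 to +64 points.

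If both groups truly have a 70% rate, the 3 v 17 Wald interval excludes zero in 30% of trials. In 28% of trials it does so while Fisher p > 0.05.

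**The case against.** - **The low coverage depends on chosen rates.** This stands. No document suggests that the single-treatment group of 3 has three times the risk of the others, and reversing the rates raises coverage to 82% (3 v 10) and 91% (3 v 17). A reader might take 35% as what these limits deliver, or as the worst case. Neither is supported: coverage is 98–99% at 5% in both groups, and 29% for 3 v 10 at 5% v 2%.
- **The scope is narrower than it looks.** This stands in part. The sentence sits in the adverse-event paragraph. A reader might infer that it governs every binary contrast, including HbA1c response and procedure success. The wording permits that but does not say so, and on a narrow reading those endpoints fall under the exact rule. The 70% scenario, and 3/3 v 10/17 as a responder result, rest on the wider reading. The between-group safety contrasts are covered on either reading.
- **Other methods carry the comparison.** The protocol uses Fisher's test and SAP 9.1 a logistic model. But the test gives a p-value and the model works on the logit scale. Neither supplies an interval for a risk difference.
- **Little depends on these limits.** This largely stands. SAP 7.1 calls the testing informative only, the stopping rules in Protocol 4.5 do not use intervals, and x/N is shown for each group. A group result of 0/3 would carry an exact upper limit of 70.8%, so a careful reader would see that [0, 0] says little.

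**Conclusion.** The defect is real but confined to between-regimen differences in proportions. As written, the rule gives zero-width limits whenever both groups are at 0% (or both at 100%). Away from equal low rates, its coverage can fall far below nominal. The size rests on an inferred 95% level, no continuity correction and assumed true rates.

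A reader might conclude that the primary safety result is compromised. The documents do not support that. SAP 9.1 first asks for a single overall percentage, which keeps an exact interval (0/20 would have an upper limit of 16.8%), and the single-group adverse event intervals are exact too. The study is descriptive, with no power basis and no decision tied to these limits. The point should be fixed before analysis, but it does not invalidate the plan.

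**What to change.** Replace the sentence in SAP section 7 with wording such as:

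> *Two-sided 95% limits for between-group differences in proportions will be exact unconditional (score-based) limits, or Newcombe or Miettinen–Nurminen score limits, including when both groups are at 0% or at 100%. Wald limits will not be reported.*

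The final text should name one of these methods. It should also state whether the rule covers the binary secondary endpoints as well as adverse events.

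The cost is one sentence and a small programming change; design and data collection are untouched. The intervals will usually be wider: for 0/3 v 0/17, exact unconditional limits are about −24 to +71 points. Score limits remain approximate. Newcombe's minimum coverage is 89–91% over true rates from 5% to 95%, and at 1/3 v 0/17 it excludes zero although Fisher p = 0.15. Occasional disagreement with Fisher's test will therefore remain, and the report should say so.

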# 7.1. Multiple Comparison/Multiplicity

This is a feasibility study and the hypothesis testing that is being performed is strictly for informative purposes. There will not be any adjustment for multiplicity.

## 7.2. Adjustments for Covariates and Stratification Factors

Data will be presented by individual subgroups if there are a sufficient number of patients to warrant the breakdown. There are no planned stratification factors to be included in the models of the 5 different Comparison Sets.

# 7.3. Handling of Missing Data

# 7.3.1. Missing and Censored Data

All tabulations and analyses will be based on the observed data without imputation, with the exception of dates.

